2. **eReferral**, the second intervention, is a new technologically-advanced, automated strategy that links hospital EHRs to a quitline via a bi-directional connection¹¹ using Direct, a national encryption standard for securely exchanging clinical healthcare data (**Figure 3**). Quitlines offer free cessation support (counseling and often an NRT sample) to U.S. smokers who call a toll-free number.^{13,14} Proactive telephone counseling is an efficacious smoking cessation treatment method that incorporates motivational interviewing, cognitive-behavioral counseling, and relapse prevention strategies, usually in a multi-session call format.^{9,91,92} For the study, the RA enrolling the patient will make the eReferral from the EHR at discharge. Quitline staff will then attempt to contact the smoker by phone within 72 hours to offer the standard services offered by the state quitline (multiple-call counseling protocol and 4 weeks NRT).^{12,73} Up to 3 contact attempts are made but in practice successful connection may take several weeks. A report of the quitline referral is sent securely to the EHR where the patients’ primary health care team can access it and act upon it as needed. In accordance with best practices for Federal Health IT as determined by the Office of the National Coordinator for Health Information Technology, eReferral employs standardized recommendations for message structure, content, transport, and delivery to maximize interoperability. The standardized data elements facilitate quality improvement and reporting metrics for NHQM. The quitline provider for this study, National Jewish Health (NJH), currently serves all MA and PA patients under state contract⁹³ and will also serve Vanderbilt study participants to ensure uniformity of eReferral across sites.

VI. BIOSTATISTICAL ANALYSIS

Data Collection

Baseline data: Each site’s RA will do a baseline survey after enrollment and collect contact information for the patient and up to 3 close contacts in order to minimize loss to follow-up. To minimize burden on hospitalized subjects, some data will be obtained from hospital records and the standardized data collection

Figure 3: eReferral Process

form used by smoking counselors who provide inpatient counseling at each site. Smoking counselors and RAs will be trained to ensure that they complete data forms consistently across all sites.

Blood collection for future potential genetic analyses (Vanderbilt site only): The NIH's precision medicine initiative, All of Us, aims to understand how genetics, in conjunction with a person's environment and lifestyle, can optimize prevention and treatment of illness. The GSCAN results recently published in *Nature Genetics*¹¹⁵ identified hundreds of new genetic variants related to smoking initiation, rate, maintenance, and cessation. New information continues to become available regarding the role of genetic variation in smoking cessation and response to pharmacotherapy. The Vanderbilt University Medical Center (VUMC) site study staff will initiate a protocol to collect a blood sample on newly-enrolled and consented participants for genotyping (GWAS). The updated informed consent document thoroughly incorporates language recommended by NIH guidelines for genetic studies https://osp.od.nih.gov/wp-content/uploads/NIH_GDS_Policy.pdf. For participants who consent to provide a genetic sample, a single blood sample of approximately 15 ml (3 teaspoons) will be collected at the bedside by clinical phlebotomy/study staff.

Outcome assessment: Outcome assessments for all sites will be conducted at 1, 3, and 6 months after hospital discharge by RedCap-initiated surveys, MGH-based study staff, and mailed survey (6-month). In response to the coronavirus, a separate RedCap survey will be administered to all patients enrolled in the study who have not withdrawn or died to explore the impact of coronavirus on tobacco use behaviors and related constructs. Study participants will receive \$20 uploaded to their payment card for completing this optional coronavirus survey. Study participants will select preferred method/s of contact (Participant Contact Sheet). RedCap follow-up surveys will be accessible through a password protected link sent to subjects by email and/or text message. Subjects can click on the link via computer or mobile device. Participants who do not complete the assessment by email or text, will be contacted by MGH study staff and mailed survey (6-month survey only). If participants cannot be reached, study staff will reach out to subjects' alternate contacts to find newer contact information. Subjects will receive \$20 uploaded to their payment card (provided at enrollment) for each follow-up assessment completed. An additional audio-recorded qualitative survey will be offered to participants at 3- and 6-months to solicit feedback about participants' experience in participating in the study.

In addition to the HH4 Quantitative COVID Survey and HH4 Qualitative Interview (AMEs 36-38), study investigators will leverage the parent study's existing partnership with the large US state quitline operator, National Jewish Health (NJH) to address much larger population-based statewide samples. Approximately 16,000 individuals, during a one-year period, who smoke and/or vape and who are calling their state quitline in Massachusetts (MA), Pennsylvania (PA), Kentucky (KY), and Minnesota (MN) for help during the pandemic will be asked 3 questions to assess COVID-19 pandemic-related effects on their *risk perceptions, motivation, and smoking and/or vaping behavior*. These questions harmonize with the existing HH4 Quantitative COVID Survey. Survey questions will be administered by trained quitline staff as part of the standard intake process (web or phone).

Data will be maintained by NJH with permission of the Departments of Health in each state, who consider the COVID-19 related survey questions to be part of quitline care (i.e., not requiring informed consent). The HH4 team will analyze de-identified aggregated state quitline data provided by NJH. With quitline data, investigators will explore the impact of coronavirus on individuals' *risk perception, change in motivation to quit, change in tobacco use, and engagement in treatment resources*, as well as explore 6-month quit rates during the pandemic as compared to 1 year earlier, adjusting for any imbalance in caller characteristics.

Measures

Intervention Effectiveness: Smoking Cessation

1° Outcome measure: Verified 7-day point prevalence tobacco abstinence at 6-month follow-up

The proposed measure is self-reported abstinence from all tobacco products (including electronic cigarettes) for the past 7 days, confirmed by a saliva cotinine of ≤ 10 ng/ml or CO <9 ppm, which are consensus values.^{96,97} We will obtain saliva samples by mail, an accepted method.⁹⁸ Our definition of tobacco abstinence does not allow for e-cigarette use because the FDA has deemed e-cigarettes to be tobacco products⁹⁹, but it allows for NRT use, as recommended.⁹⁶ Because of uncertainty about the risk/benefit of e-cigarettes for cessation, we will calculate a secondary tobacco abstinence measure that allows for use of e-cigarettes but no other tobacco products. (In the HH2 trial, the alternative calculation produced very small differences in abstinence rates that

did not change study results.) Because NRT use produces a false positive cotinine, the biochemical validation criterion for a patient reporting NRT use at 6 months will be an expired-air carbon monoxide measurement of <9 ppm, obtained at an in-person visit.¹⁰⁰ Subjects who self-report smoking, do not provide a saliva sample or CO measurement, whose cotinine or CO measures exceed the cut-offs, or who are lost to follow-up at 6 months will be counted as smokers.^{96,97,100} Obtaining saliva samples in low-contact intervention trials, including recent studies in hospitalized smokers, is challenging.^{55,101} We will offer a \$150 incentive uploaded to their payment card for return of a sample, which produced a 69% return rate in HH2 (with no difference by study arm).

2^o Outcome measures of tobacco use: to be calculated using standard definitions.⁹⁶

- Self-reported 7-day and 30-day point prevalence tobacco abstinence at 1 month, 3 months, 6 months
- Sustained [repeated point prevalence] tobacco abstinence (= self-reported abstinence at 1, 3, and 6 months)
- Duration of continuous tobacco abstinence after hospital discharge (self-report)

Engagement in Tobacco Cessation Treatment

- Proportion of participants who use smoking cessation counseling or pharmacotherapy after discharge
- Duration (days) of medication use, number of counseling contacts after discharge

Definitions: Counseling can be from any evidence-based source, including clinicians, and occur in person, by phone or text message. Neither quitline registration calls nor IVR calls will be counted as counseling, but speaking to a tobacco coach at either the quitline or hospital will count. Medication includes all FDA-approved smoking cessation medications.

To succeed in promoting tobacco abstinence, post-discharge interventions must engage patients in tobacco treatment. To do so, they must reach patients after discharge, and patients must agree to use evidence-based pharmacotherapy and/or counseling. **Table 3** shows how we will measure these concepts, using a combination of patient self-reports at each assessment and records of treatment offer or delivery obtained from TelASK (IVR vendor), NJH (quitline), and SmokefreeTXT internal monitoring systems as well as from the EHR. EHR data will include (1) quitline feedback reports; (2) tobacco coach records of patient contact and coordination of care activities; (3) pharmacy records of NRT prescriptions provided by the study; (4) use of SmokefreeTXT. (Usage data from SmokefreeTXT will be visible to the tobacco coach in the EHR through the Epic-Smokefree.gov interface that is currently being programmed and will be publically available by 2017 (*personal communication with [name], Smokefree.gov Director*). This approach utilizes the capacity of EHRs to capture data on tobacco treatment use for assessing the outcomes of interventions and illustrates how tobacco treatment interventions can be integrated into EHRs.

Table 3: Treatment engagement / use measures

Post-discharge Interventions	Personalized Tobacco Care Management (PTCM)			eReferral to Quitline (eReferral)		
	Measure	Data sources		Measure	Data sources	
		Surveys	Other source		Surveys	Other source
Outreach contact	% complete any IVR/Email/TXT contact # of IVR/ Email/TXT contacts completed	x n/a	Vendor records	% reached by QL	x	QL report (EHR)
Treatment Use - Medication	% given NRT at d/c Duration of NRT use, other med use	x x	EHR records	% given NRT at d/c % sent NRT sample % receive NRT	x	EHR records QL report (EHR)
- Counseling	% talk to coach, # of calls completed	x n/a	EHR records	% enroll in counseling	x n/a	QL report (EHR)

	% referred to QL or SmokefreeTXT Usage details of QL, SmokefreeTXT	x	EHR records QL/TXT records	# of calls completed		
--	---	---	-------------------------------------	-------------------------	--	--

Health and health care utilization outcomes

All-cause hospitalizations, cardiac and respiratory hospitalizations, all-cause deaths over 1 year. We will compare rates of hospitalizations and mortality in the two study arms. These will be secondary, exploratory analyses. There is some evidence that hospital-initiated tobacco treatment programs can reduce readmissions by 30 days and mortality by 1 year follow-up.³⁸ At all follow-up surveys, we will ask subjects about subsequent hospital admissions, using standard items from the National Health Interview Survey. To corroborate patient reports, we will review administrative data from our hospitals and ask permission to review the discharge summaries from any admission to an outside hospital. Among subjects lost to follow-up, mortality will be detected via proxy contacts, by reviewing hospital records, and, if necessary, the National Death Index.

Covariates (moderators) - All done at baseline. [* = also repeated at follow-ups.]

- Sociodemographic: age, sex, education, race, ethnicity, marital status, employment, health insurance type.
- Smoking history and behavior: cigarettes/day (month before admission), intention to remain abstinent after discharge (5-point Likert scale), years smoked, past >24 hour quit attempt (ever, in past year), past use of treatment (FDA-approved meds, counseling by phone, text message, website, physician).
- Nicotine dependence: Fagerström Test for Nicotine Dependence (6-items).¹⁰²
- Self efficacy to quit: importance, confidence in ability to quit (1 item each, 5-point Likert scale).^{80,103}
- Medical history (from hospital record): tobacco-related diagnoses CHD, COPD, stroke, cancer; CVD risk factors (hypertension, diabetes, hyperlipidemia).
- Hospital course (from hospital record): primary and secondary discharge diagnoses, length of stay.
- *Depressive symptoms: 8-item Center for Epidemiologic Studies Depression Scale¹⁰⁴ at baseline and follow-up. Rationale: depression is common in smokers,¹⁰⁵ depressive symptoms predict post-discharge relapse.¹⁰⁶
- *Alcohol use: AUDIT-C,¹⁰⁷ a 3-item survey assessing frequency, quantity, and binge drinking. Rationale: heavy alcohol use is associated with difficulty quitting.
- *Other substance use: Any past month use. Rationale: other substance use is common in smokers and may be associated with lower quit rates after treatment.

Implementation and Process Measures. Data at each site will be collected to monitor rates of study eligibility, refusal, intervention delivery, and follow-up completion, using the following RE-AIM model constructs.¹⁰⁸ Reach: % of identified smokers admitted during the study who are seen by a TTS counselor, are eligible for the study, and enroll. Effectiveness: the 1^o trial outcome. Implementation: % of subjects assigned to each study arm who receive relevant components (See Table 3). These data will be obtained from TelASK, NJH, and SmokefreeTXT internal monitoring systems as well as from the EHR.

Statistical methods

Sample Size

A total sample of 1350 (675/group) will have 84% power to detect a 6.5% absolute difference in primary outcome, verified 7-day point-prevalence abstinence at 6 months, assuming rates of 16.5% (eReferral group) and 23% (PTCM group), and a 2-tailed type I error rate of .05. The rate ratio (1.39 = .23/.165) is clinically meaningful and resembles the ratio found in the Cochrane meta-analysis of smoking cessation interventions for hospitalized patients.² **Rationale:** eReferral: We conservatively estimate the abstinence rate from the HH trial (17% and 16%)⁵⁶; patients in both conditions were referred to a quitline. PTCM: Intervention resembles that of HH1 (25% abstinence rate);³⁹ we conservatively estimate 23%.

VII. RISKS AND DISCOMFORTS

The potential risks to subjects include potential psychological distress from speaking with a counselor or answering questions about their smoking, and a loss of confidentiality of their healthcare data. In addition,

those patients who are randomly assigned to receive a free supply of FDA-approved smoking cessation medication may be subject to the potential side effects of using nicotine replacement therapy (NRT).

- Nicotine patch: The most common side effect is irritated skin where the patch is applied, which is commonly managed by rotating patch sites and/or applying an OTC corticosteroid cream (such as 1% hydrocortisone). In rare cases nausea, dizziness, tachycardia can occur. Nicotine patches are sold without prescription in the U.S., which is an indication of the FDA's view of their relative safety.
- Nicotine gum or lozenge: The most common side effects are sore jaw, sores in the mouth, hiccups, dyspepsia, and nausea. In rare cases nausea, dizziness, or tachycardia can occur. Many of the side effects of the gum are the result of chewing the gum improperly and can be avoided by proper technique of the gum. Nicotine gum and lozenges are sold without prescription in the U.S., which is an indication of the FDA's view of their relative safety.

Other risks:

Participants are at some risk for loss of privacy/confidentiality. If patients opt to receive phone calls on a shared phone, a family member may inquire about the nature of the phone calls. Study staff will not disclose information about participants' participation in the study to others who share a phone line with participants. They will leave the minimum amount of information necessary on participant answering machines.

There is a risk of counseling bringing up issues that are upsetting to participants. Counselors will do their best to be supportive to patients. In addition, participants will be told that they can refuse to answer any questions or terminate contact with counselors at any time.

VIII. POTENTIAL BENEFITS

Participants in this study may benefit by being connected better to effective tobacco treatment resources after hospital discharge. They will receive up to 8 weeks of FDA-approved smoking cessation medication at no cost. As a result, they may be helped to quit smoking. Generally, there is nothing better for smokers' health than stopping smoking.

IX. MONITORING AND QUALITY ASSURANCE

Data Monitoring Plan: Study staff will provide TelASK Technologies, Inc., the vendor who will conduct outreach attempts via IVR call/email/text message with patient names and relevant contact information. This information will be transferred bi-directionally through a secure FTP. During the study, TelASK will establish a secure website interface to the data management system in which study staff can view outreach and outcome results in real time.

Data quality (including visits completed during intervention window, missing data, and recruitment rates) will be monitored monthly by the database manager, [name], and systemic data problems will be reported to the PI. IVR calls, emails, and text messages provided by TelASK, Inc. will be monitored for quality assurance. In addition, the Project Manager will review 10% of the counseling progress notes for adherence to the protocol. Outcomes data will be analyzed by [name], a biostatistician, using logistic regression and survival analysis. The alpha level will be set at 5%. Interim data analysis will be conducted halfway through the trial and results will be reported in the annual NIH progress report.

The principal investigator, [name], and the Project manager will be responsible for monitoring the safety and effectiveness of this trial, executing the data safety and monitoring (DSM) plan, and complying with reporting requirements. [name] will supply a summary of the DSM report to the NIH on an annual basis as part of the progress report.

Safety Monitoring Plan: The main risks to participation in the study include the potential for psychological discomfort during counseling sessions and side effects to the FDA-approved medications. We will protect against risks of psychological discomfort by using language that is meant to offer assistance and promote health, rather than demonstrate blame or guilt. In order to protect against risk from pharmacotherapy usage, these steps will be taken:

(1) Medication is being provided only to patients in the PTCM intervention arm. These participants also receive automated telephone calls by IVR 7 times in the 3 months after hospital discharge, especially soon after discharge (at 3 days and 2, 4, 6, 8, 10, and 12 weeks). At each call, patients are specifically asked about any side effects or problems. Those who report them are advised to speak to a live tobacco counselor. Patients who request a medication refill after the initial 30 day supply are required to speak to a live counselor, who asks about medical problems before authorizing a refill of medication. Study staff will be required to report any unexpected or questionable reports of adverse effects to the study PI ([name]). These will be reviewed at the weekly study staff meeting. If more urgent, the PI will review immediately.

(2) The study PI ([name]) will review provide back up to study staff for all medical questions that arise during participant enrollment or study progress.

(3) The study PI ([name]) will review any serious adverse events and report them appropriately to the IRB. SAEs that represent hospital readmissions are anticipated to be frequent in this population of patients with medical illness. Each will be reviewed by the study PI to ensure that the readmission is not related to study medication.

Adverse Events Reporting: Participants who report any adverse events to the smoking counselor will be advised to discuss these side effects with their doctor. The reports of the adverse events will be summarized and reviewed by the PI on a monthly basis and reported to the IRB upon renewal of approval and to the funding agency upon continuing review. Serious adverse events will be reported immediately to the PI who will contact the participant, the participant's physician and the IRB.

X. REFERENCES

1. U.S. Department of Health and Human Services. *

The health consequences of Smoking—50 years of progress: A report of the surgeon general.* . Atlanta (GA): Centers for Disease Control and Prevention, National Center for Chronic Disease Prevention and Health Promotion (US) Office on Smoking and Health; 2014. <http://www.surgeongeneral.gov/library/reports/50-years-of-progress/index.html>. Accessed 11/25/15. NBK179276 [bookaccession].
2. [name] NA, Clair C, Munafo MR, Stead LF. Interventions for smoking cessation in hospitalised patients. *Cochrane Database Syst Rev.* 2012;5:001837.
3. [name] NA, Munafo MR, Stead LF. Smoking cessation interventions for hospitalized smokers: A systematic review. *Arch Intern Med.* 2008;168(18):1950-1960.
4. Centers for Disease Control and Prevention (CDC). Cigarette smoking among adults and trends in smoking cessation - united states, 2008. *MMWR Morb Mortal Wkly Rep.* 2009;58(44):1227-1232.

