Specific Aim: To conduct a randomized controlled comparative effectiveness trial of two strategies to promote smoking cessation in hospitalized patients: (1) Personalized Tobacco Care Management (PTCM) offering smokers 8 weeks of free nicotine replacement therapy (NRT) in hand at discharge and 7 proactive automated contacts over 3 months via interactive voice response (IVR) phone calls followed by email and/or text message and (2) eReferral, a one-time automated referral from the EHR to the state quitline at discharge. The proposed randomized controlled trial will enroll 1350 adult smokers admitted to 3 large hospital systems in 3 U.S. regions (MA, PA, TN) selected to vary in size, type, and region in order to demonstrate the intervention model's potential for dissemination. All patients will receive guideline-based tobacco cessation treatment delivered in-hospital by each site's existing Tobacco Treatment Service²³ directed by a team member (Drs. [name], [name], [name]). At discharge, subjects will be randomly assigned to PTCM vs. eReferral and followed at 1, 3, and 6 months.

Aim 1: To increase tobacco abstinence among hospitalized smokers after hospital discharge.

Hypothesis 1: PTCM, vs. eReferral, will increase the proportion of smokers with biochemically-validated 7-day point prevalence tobacco abstinence at 6 months after hospital discharge (1^o outcome measure).

Aim 2: To increase hospitalized smokers' engagement in tobacco cessation treatment after discharge.

Hypothesis 2: PTCM, vs. eReferral, will increase the proportion of smokers who are using smoking cessation treatment (counseling and/or medication) at 1 month and 3 months after hospital discharge.

Aim 3: To assess the incremental cost-per-quit, comparing PTCM and eReferral.

Hypothesis 3: PTCM will cost more and be more effective than eReferral, but the incremental cost per quit will compare favorably to other tobacco cessation interventions (<=\$5000/quit).

Exploratory Aims: Additionally, we will explore the interventions' effect on health and health care utilization (mortality and hospital readmissions, respectively) 5-years post-discharge, and assess implementation fidelity of both arms.

[figure not shown]
COVID-19 Quitline Data Specific Aims:

Aim 1: To assess the effect of the COVID-19 pandemic on current cigarette smokers' health perceptions, smoking behavior, efforts to quit smoking, and engagement in treatment resources.

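### Deaths and hospitalizations are compared beyond the last scheduled contact at 6 months, but the stated death search covers only participants lost to follow-up

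*Combined protocol and SAP*

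**What the plan says.** Under Outcome assessment (section VI): "Outcome assessments for all sites will be conducted at 1, 3, and 6 months after hospital discharge". An optional coronavirus survey may reach some participants later, but no items on admissions or deaths are described for it.

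Under Health and health care utilization outcomes (section VI, Measures), the outcomes are "All-cause hospitalizations, cardiac and respiratory hospitalizations, all-cause deaths over 1 year". The protocol adds "We will compare rates of hospitalizations and mortality in the two study arms" and "These will be secondary, exploratory analyses". The Exploratory Aims in section II give a different horizon: "mortality and hospital readmissions, respectively) 5-years post-discharge".

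The sources are set out in the same Measures paragraph:

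- **Hospitalizations.** "At all follow-up surveys, we will ask subjects about subsequent hospital admissions". The second source is secondary by its wording: "To corroborate patient reports, we will review administrative data from our hospitals". No time window is given for that review. Discharge summaries from outside hospitals need the participant's permission.
- **Deaths.** "Among subjects lost to follow-up, mortality will be detected via proxy contacts, by reviewing hospital records, and, if necessary, the National Death Index". No search is stated for anyone else, and the paragraph does not define loss to follow-up for these outcomes.

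**The concern.** Half of the 1-year window, and 54 of the 60 months of the 5-year window, fall after the last scheduled assessment. In that period the stated rules treat participants differently according to whether they kept answering surveys. Someone who stopped responding at month 3 and died at month 9 is in the group to be searched. Someone who completed month 6 and died at month 9 is not.

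Survey completion happens after randomization. The arms also differ in how much contact they provide: seven automated contacts and a hospital-based coach in PTCM, against a one-time referral in eReferral. If that difference affects retention, the better-retained arm has fewer of its late deaths searched for and appears to have lower mortality without any true effect.

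For hospitalizations, self-report stops at month 6, so there is no later patient report to corroborate and no stated way to see an admission elsewhere.

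**Working it through.** **The plan's own figure.** The only design calculation is for verified abstinence: 675 per arm, 16.5% versus 23%, two-sided 0.05, 84% power. With pooled variance under the null, SE0 = √(2 × 0.1975 × 0.8025/675) = 0.02167 and SE1 = √((0.165 × 0.835 + 0.23 × 0.77)/675) = 0.02160. Power = Φ((0.065 − 1.96 × 0.02167)/0.02160) = 85.2%, which agrees with 84% to within about a point. No event rate or power is given for deaths or hospitalizations, so the rest is an illustration.

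**Inputs.** The preceding trial (Helping HAND 2, under Preliminary Work) assessed 75% of enrollees at 6 months, and no breakdown by arm is given. The retention splits below are assumptions centred on 75%. True mortality is assumed equal in the two arms.

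**Formula.** Let f be the proportion completing month 6, s the chance that the search finds a death among those lost, and c the chance that a completer's late death is found. The share of late deaths detected is (1 − f)s + f·c.

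**Literal reading (s = 1, c = 0).** The ratio for deaths after month 6 is (1 − f_PTCM)/(1 − f_eReferral). For 1 year, assume that half of deaths fall in each half-year and that those before month 6 are all found, since those participants cannot complete the 6-month survey. The ratio becomes [1 + (1 − f_PTCM)]/[1 + (1 − f_eReferral)].

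| Retention, PTCM / eReferral (assumed) | After month 6 | Over 1 year |
|---|---|---|
| 75% / 75% | 0.25/0.25 = 1.00 | 1.25/1.25 = 1.00 |
| 77% / 73% | 0.23/0.27 = 0.85 | 1.23/1.27 = 0.97 |
| 78% / 72% | 0.22/0.28 = 0.79 | 1.22/1.28 = 0.95 |
| 80% / 70% | 0.20/0.30 = 0.67 | 1.20/1.30 = 0.92 |

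At 75% retention in both arms, 75% of deaths after month 6 are missed, or 0.5 × 75% = 37.5% of 1-year deaths, although the ratio is undistorted.

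**If hospital records find some completers' deaths (s = 0.95, assumed).** For deaths after month 6 at 80% / 70%:

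- c = 0.3: (0.20 × 0.95 + 0.80 × 0.3)/(0.30 × 0.95 + 0.70 × 0.3) = 0.430/0.495 = 0.87
- c = 0.6: (0.190 + 0.480)/(0.285 + 0.420) = 0.670/0.705 = 0.95

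At 78% / 72% the corresponding ratios are 0.92 and 0.97.

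**Counts.** The ratios do not depend on the mortality rate. If 4% of each arm died between months 6 and 12 (assumed), there would be 675 × 0.04 = 27 late deaths per arm. The literal reading at 80% / 70% would detect 27 × 0.20 = 5.4 against 27 × 0.30 = 8.1. Rates of 2% to 6% give 13.5 to 40.5 true late deaths per arm.

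**After the fix (s = c).** The detected share is s in both arms whatever f is. With s = c = 0.95 (assumed), 5% of late deaths are missed in each arm and the ratio is 1.00 at every split.

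**The case against.** A reader might infer that late events will be missed and that the mortality comparison will favour PTCM. The document does not establish either.

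- The administrative review has no stated cutoff and sits under an outcome defined over 1 year. It could find late readmissions, and deaths in the study hospitals, among completers. The preceding trial used administrative data to 12 months for the same outcomes. This protocol does not say it will do so, but ending the review at month 6 is only one reading.
- Loss to follow-up is tied to 6 months where the smoking outcome is defined, but not here. If anyone whose vital status is unknown at 1 year counts as lost, the gap narrows or closes.
- Retention by arm is not reported. Follow-up methods and survey payments are the same in both arms, and equal retention leaves the ratio at 1.00.
- The ratios of 0.67 to 0.85 apply only to deaths after month 6 with nothing found among completers. The planned 1-year outcome dilutes them to 0.92 to 0.97 under the even split. Dilution would be weaker over 5 years.
- For hospitalizations, a reader might infer bias between arms. Randomization is stratified by site, and nothing suggests that the share of readmissions to study hospitals differs by arm.

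All of this limits the size of the problem. It does not supply a stated death search for 6-month completers or a source for outside admissions after month 6. That the wording permits several readings is itself a reason to settle it.

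**Conclusion.** The gap is real and modest. As written, the only stated death search is conditional on a post-randomization variable, and the comparison extends 6 to 54 months past the last scheduled assessment, depending on which horizon applies. Undercounting of late deaths follows from the literal reading. Bias between arms needs unequal retention as well, which is plausible but undocumented. Under the assumed 78% / 72% and 80% / 70% splits, with no detection among completers and deaths split evenly between half-years, the 1-year ratio is about 0.95 and 0.92. It moves closer to 1 as records find more completers' deaths. For hospitalizations the supported conclusion is an undercount of outside admissions after month 6. These outcomes are exploratory, and the abstinence analysis and its sample size stand as they are.

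**What to change.** - Reconcile the 1-year and 5-year windows and state one.
- Apply the same hospital-record and National Death Index search to every randomized participant in both arms, through one fixed time after discharge, whatever their survey status.
- Make study-system administrative data for all participants the primary source for hospitalizations after month 6, and report them as study-system admissions only.
- Report self-reported outside admissions only through month 6.

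The sources are ones the plan already names, and no visit or sample-size change is needed. The costs are an index search of up to 1350 people instead of the lost subset, and a narrower definition of hospitalization after month 6. The document gives neither the search fee nor the identifiers available for matching. The only Social Security number collection it describes is for payment and with permission, so feasibility for all participants should be checked first.
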